4.3. Inclusion Criteria

- Subjects must be generally healthy and 25-65 years of age at Screening Visit
- 2. Subjects who have:

mild to significant volume deficit in the mid-face (score of 2-4 on the designated photographic assessment scale (see section 5))

or

mild to moderate jawline ptosis (score of 1-2 on the designated photographic assessment scale (see section 5))

or

minimal to severe chin retrusion (score of 1-3 on the designated photographic assessment scale (see section 5))

or

minimal to severe temporal hollowing (score if 2-4 on the designated photographic assessment scale (see section 5))

- 3. Subjects who are willing to provide written informed consent, including approval for facial photographs to be taken.
- 4. Subjects willing to commit to having no further facial aesthetic treatments (see Table 2) for the duration of the study period, including follow-up.
- 5. Subjects must be willing and able to comply with protocol requirements, instructions, and protocol-stated restrictions and be likely to complete the study as planned.

6. Female of childbearing potential should use a medically accepted contraceptive regimen since at least 12 weeks prior to study entry and during all the study

4.4. Exclusion Criteria

- 1 Subjects who, in the twelve months prior to their enrolment assessment had undergone:
 - a. cosmetic facial plastic surgery (other than rhinoplasty),
 - b. tissue grafting (e.g., fat injections),
 - c. tissue lifting implants (e.g., threads, barbs) or other implants,
 - d. augmentation with any permanent or semi-permanent filler (e.g., silicone, PMMA, PLLA) or temporary filler (e.g., Ha, CaHA, PCL)
 - e. neuromodulator injections,
 - f. mesotherapy,
 - g. resurfacing in the mid-face (e.g., laser, radio frequency, dermabrasion, or chemical peel)

in the region of the face to be treated.

2 Subjects who have received any other facial aesthetic procedures (as described at exclusion criteria 1) at any time during the study period (see Table 2).

Table 2: MaiLi Volume and Extreme - Non-allowable treatments

Subject treatment area	No further aesthetic treatments are allowed in the region of:	Reason		
Mid-face	Nasolabial folds Nose	Adjacent to treatment area Effect on facial appearance is too significant		
	Tear troughs Prejowl sulcus Nasojugal folds	Area assessed within mid-face scale Area assessed within mid-face scale Area assessed within mid-face scale		
Jawline/Jowls	Nose Pre-jowl sulcus Marionette lines	Effect on facial appearance is too significant Adjacent to treatment area Adjacent to treatment area		
Chin	Nose Platysma Pre-jowl sulcus Lips	Effect on facial appearance is too significant Adjacent to treatment area Adjacent to treatment area Lips are reference points for chin scoring scale		
Temples	Nose Periorbital lines Forehead	Effect on facial appearance is too significant Adjacent to the treatment area Adjacent to the treatment area		

- 3 Subjects currently enrolled in other clinical trials.
- 4 Subjects with facial hair as this could interfere with study evaluations.
- 5 Subject who had been deprived of their freedom by administrative or legal decision or who is under guardianship.
- 6 Subject is an employee of the aesthetic surgery department of the investigational site, the CRO or study sponsor.
- 7 Pregnant or nursing woman or planning a pregnancy during the study.
- 8 Subjects taking thrombolytics or anticoagulants.
- 9 Subjects with bleeding disorders.
- 10 Subjects with known hypersensitivities to hyaluronic acid, lidocaine. amide local anaesthetics or other components of the treatment.
- 11 Subjects with a history of severe allergy or anaphylactic shock.
- 12 Subjects with active (or a history of) autoimmune disease.
- 13 Subjects with porphyria.
- 14 Subjects with cutaneous disorders and areas affected by inflammation and/or infectious skin problems (e.g., acne, herpes) at or near the treatment site
- 15 Subjects with a tendency to form keloids, hypertrophic scars or any other healing disorders
- 16 Subjects with known history of precancerous lesions/skin malignancies.
- 17 Subjects must avoid receiving COVID-19 vaccination for the 14 days before and following injection.

STUDY DESIGN AND PROCEDURES/METHODOLOGY

The study is a 24-month, open-label, prospective, post-market clinical follow-up trial, conducted in compliance with ISO 14155:2020, the International Conference on Harmonization (ICH), and Good Clinical Practice (GCP) principles. The trial will be approved by the ethical committee of the participating sites and complied with local regulatory authority requirements. Following the guidelines of the European Standard for Aesthetic medicine services-non-surgical medical treatments, which lists the allowed aesthetic procedures, premises, and training requirements to conduct aesthetic procedures for doctors.

Potential subjects who visit the clinic for aesthetic procedures will be explained about the study by the investigators for recruitment and informed consent will be taken from the subjects before the study procedures.

Potential subjects will first be registered at the clinic. The investigator will explain the study to the subjects, including details of the treatment procedure and the associated benefits and risks. The subjects will be given time to read the consent form and clarify any questions they have about the study with the investigator. The subject should be informed of the product's indications, contraindications, precautions, warnings, expected results, and potential adverse events and questioned on her/his medical history. In addition, the subject must be given the option to indicate whether he/she would like to remain unidentifiable in the photographs (through the use of a black box) and whether the photographs may be used for publication and promotion of the medical devices.

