- 1. Subjects must be generally healthy and 25-65 years of age at Screening Visit
- 2. Subjects who have:

mild to significant volume deficit in the mid-face (score of 2-4 on the designated photographic assessment scale (see section 5))

or

mild to moderate jawline ptosis (score of 1-2 on the designated photographic assessment scale (see section 5))

or

minimal to severe chin retrusion (score of 1-3 on the designated photographic assessment scale (see section 5))

or

minimal to severe temporal hollowing (score if 2-4 on the designated photographic assessment scale (see section 5))

- 3. Subjects who are willing to provide written informed consent, including approval for facial photographs to be taken.
- 4. Subjects willing to commit to having no further facial aesthetic treatments (see Table 2), that could affect the appearance of the facial treatment area, for the duration of the study period, including follow-up.
- 5. Subjects must be willing and able to comply with protocol requirements, instructions, and protocol-stated restrictions and be likely to complete the study as planned.
- 6. Female of childbearing potential should use a medically accepted contraceptive regimen since at least 12 weeks prior to study entry and during all the study.

Exclusion Criteria

Subjects meeting any of the following criteria will be excluded from the study:

- 1. Subjects who, in the twelve months prior to their enrolment assessment had undergone:
 - a. cosmetic facial plastic surgery (other than rhinoplasty),
 - b. tissue grafting (e.g., fat injections),
 - c. tissue lifting implants (e.g., threads, barbs) or other implants,
 - d. augmentation with any permanent or semipermanent filler (e.g., silicone, PMMA, PLLA) or temporary filler (e.g., Ha, CaHA, PCL)
 - e. neuromodulator injections,
 - f. mesotherapy,
 - g. resurfacing in the mid-face (e.g., laser, radio frequency, dermabrasion, or chemical peel)

in the region of the face to be treated.

2. Subjects who have received other facial aesthetic procedures, that affects the appearance of the facial treatment (see Table 2 in Protocol), at any time during the study period.

- 3. Subjects currently enrolled in other clinical trials.
- 4. Subjects with facial hair as this could interfere with study evaluations.
- 5. Subject who had been deprived of their freedom by administrative or legal decision or who is under guardianship.

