4	Much improved	Marked improvement in appearance but not completely optimal		
5	Very much improved	Excellent corrective results		

Table 4: Assessment Scale for Mid-face volume deficit (see appendix 1²¹)

Grade	Severity	Definition				
0	None	 Moon face; Fullness (convexity) in the zygomaticomalar region, anteromedial cheek, and/or submalar region 				
1	Minimal	Flattening in the zygomaticomalar region, anteromedial cheek, and/or submalar region				
2	Mild	 Mild concavity in the zygomaticomalar region, anteromedial cheek, and/or submalar region; Mild tear troughs and/or nasolabial folds 				
3	Moderate	 Moderate concavity in the zygomaticomalar region, anteromedial cheek, and/or submalar region; Moderate tear troughs and/or nasolabial folds; Mild nasojugal folds and/or pre-jowl sulcus; Mild prominence of bony landmarks; Mild visibility of musculature 				
4	Significant	 Significant concavity in the zygomaticomalar region, anteromedial cheek, and/or submalar region; Significant tear troughs and/or nasolabial folds; Moderate nasojugal folds and/or prejowl sulcus; Moderate prominence of bony landmarks; Moderate visibility of musculature 				
5	Severe	Wasting;Severe concavity in the zygomaticomalar region,				

	anteromedial cheek, and/or submalar region;
	 Severe tear troughs and/or nasolabial folds;
	 Significant nasojugal folds and/or prejowl sulcus;
	 Significant prominence of bony landmarks;
	Significant visibility of underlying musculature

Table 5: Assessment Scale for ptosis of Jawline (see appendix 2²²)

Grade	Severity	Definition		
0	None	Continuous jawline contour, no loss of jawline volume		
1	Mild	Mild loss of jawline contour and continuity, mild loss of volume in post-jowl region, loss of volume in pre-jowl region may be present.		
2	Moderate	Moderate loss of jawline contour and continuity, moderate loss of volume in post-jowl region, loss of volume in pre-jowl may be present.		
3	Severe	Severe loss of jawline contour and continuity, severe loss of volume in post-jowl region, loss of volume in pre-jowl region may be present		
4	Extreme	Extreme disruption of jawline contour, extreme post-jowl and pre-jowl volume loss		

Table 6: Assessment Scale for Chin retrusion (see appendix 3²³)

Grade	Severity	Definition		
0	None	No chin retrusion; chin midpoint at or in front of the lower vermilion border vertical line		
1	Minimal	Minimal chin retrusion; chin midpoint is between the labiomental sulcus vertical line and lower vermilion border vertical line		

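### The 12-month look-back covers only the region to be treated, while Table 2 bars other scored or reference regions on study, so a recent procedure there can pass as treatment effect

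*Protocol*

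**What the plan says.** Exclusion criterion 1 (Protocol section 4.4, repeated in the synopsis) concerns subjects who "in the twelve months prior to their enrolment assessment had undergone" one of seven kinds of procedure. Item a is "cosmetic facial plastic surgery (other than rhinoplasty"), and the closing clause limits the whole list to procedures "in the region of the face to be treated". The protocol does not define that region for any of the four treatment areas.

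Exclusion criterion 2 and inclusion criterion 4 govern procedures during the study and refer to Table 2. Its column header reads "No further aesthetic treatments are allowed in the region of", and each row gives a reason:

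- the nose, for all four treatment areas: "Effect on facial appearance is too significant";
- tear troughs, prejowl sulcus and nasojugal folds, for the mid-face: "Area assessed within mid-face scale";
- lips, for the chin: "Lips are reference points for chin scoring scale";
- the remaining regions (nasolabial folds, marionette lines, platysma, periorbital lines, forehead, and the pre-jowl sulcus for jawline and chin): adjacency to the treated area.

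Both kinds of efficacy rating are within-subject. The on-site evaluator rates the GAIS by comparing the live face with the full-face baseline photograph (section 5). The area scales count an improvement of at least 1 point from baseline (section 2.2).

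**The concern.** Table 2 records the sponsor's view that procedures in certain neighbouring regions can affect the assessments. Criterion 1 does not clearly apply that view to the months just before baseline. A procedure one month after baseline is barred; the same procedure one month before it may be allowed, and no reason is given for the difference.

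At stake is how change from baseline is attributed. The study is open-label with no untreated group, so every change after baseline is credited to the product. If an earlier filler is wearing off, or surgical swelling is settling, that change is counted too. It could also shift the baseline grade that decides eligibility.

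**Working it through.** There is no plan figure to reproduce, so the check sets the provisions side by side.

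**Which provisions reach a recent pre-study procedure in a Table 2 region?**

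| Provision | Period | Region |
|---|---|---|
| Exclusion criterion 1 | 12 months before enrolment | region to be treated (undefined) |
| Exclusion criterion 2, inclusion criterion 4, Table 2 | during the study | wider Table 2 list |
| Section 5 warning on incompletely resorbed product of another brand | before injection | the area to be injected |

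None clearly covers the nose, the lips or the adjacent regions before baseline.

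**Do those regions enter the scores?**

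- *Mid-face (Table 4).* Grade 2 includes "Mild tear troughs and/or nasolabial folds". From grade 3, nasojugal folds and pre-jowl sulcus are graded as well. Nasolabial folds are therefore scored too, although Table 2 lists them only as adjacent.
- *Chin (Table 6).* Grade 0 places the chin midpoint at or in front of the vertical line from the lower vermilion border. Grade 1 places it between that line and the labiomental sulcus line. Grades 2 to 4 refer only to the sulcus line.

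**Worked case, chin.** Eligibility needs grade 1 to 3. Suppose the chin midpoint lies at the vermilion line, which is grade 0.

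1. Recent lip filler moves that line forward, so the chin is graded 1 and the subject is eligible.
2. The filler fades after baseline, the line moves back and the grade returns to 0.
3. That is an improvement of 1 point, so the subject is a responder on the chin scale whatever the product did.

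By the scale's definitions this happens only at the boundary between grades 0 and 1.

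**Opposite direction, mid-face.** If tear-trough filler is present at baseline and fades, the tear troughs deepen and the mid-face looks worse at follow-up. That counts against the product.

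**Stable procedures.** Let the observed change be (treatment effect + prior effect at follow-up) − (prior effect at baseline). If the prior effect is the same at both times, it drops out. Only its change between the two visits remains.

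**Weight of one subject.** Section 8.1 gives completed cohorts of 25 and 30: 1/25 = 4.0 percentage points and 1/30 = 3.3 points. This is the unit of movement, not an estimate of bias.

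**The case against.** The strongest reply is that different scopes before and during the study are coherent. Table 2 concerns procedures that fall between baseline and assessment and so cannot cancel; most earlier procedures can. This stands, and it rules out the reading that the baselines are confounded as such. A reader might infer that from the wording, but it applies only to effects still changing after baseline.

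Three further points also stand:

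- *Tear troughs and nasojugal folds.* Because the region is undefined and the mid-face scale grades these areas, an investigator may already treat them as part of the mid-face. It cannot be said flatly that such subjects are eligible. The ambiguity still lets sites screen differently, and lips cannot reasonably be read as part of the chin.
- *Rhinoplasty.* A reader might infer that the exemption itself admits these subjects. It does not. The nose is not a treated region, so the closing clause already leaves it out, and deleting the exemption alone would change nobody's eligibility. What remains is the tension with the nose rows of Table 2.
- *Timing.* The protocol does not say how long effects in neighbouring regions last. Its background section says volumising hyaluronic acids are often followed for 18 months to 2 years. Some fading may therefore fall at later visits rather than at month 6.

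Prior treatments are recorded at baseline (Table 8), and an unseen analysis plan may already use them. That would mitigate the problem but would not settle the eligibility text.

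**Conclusion.** The mismatch is real but narrow. As written, the protocol can admit a subject with a recent procedure in a region that it says is scored or used as a scale reference. If that effect is still changing after baseline, it enters the GAIS and the area scales as apparent treatment effect, in either direction. Lips for the chin are the clearest case. The nose and the merely adjacent regions are weaker cases.

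The size cannot be derived from the protocol, which gives neither the share of such subjects nor the chance that a rating changes. A reader might assume that 10–30% had such a procedure and that 20% of their ratings flip, giving 0.10 × 0.20 = 2 points to 0.30 × 0.20 = 6 points. Neither share has a source in the protocol, and the sum needs every flip to go the same way, which the two cases worked above contradict. It should not be cited as the expected bias.

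The conclusion assumes that some recruits, who are approached while attending clinics for aesthetic procedures (section 4.2), have had recent work in these regions. This is an inexpensive improvement to the plan, not a flaw that invalidates the study.

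**What to change.** 1. Define the region to be treated for each of the four treatment areas. While doing so, settle item g of criterion 1, which names resurfacing of the mid-face only and so, read literally, leaves out the jawline, chin and temple.
2. Reconcile criterion 1 with Table 2, at least so that the look-back covers the regions the protocol says are scored or used as reference points: tear troughs, prejowl sulcus and nasojugal folds for the mid-face, and lips for the chin. Decide whether nasolabial folds, which Table 4 also grades, belong in this group.
3. Reconcile the rhinoplasty exemption with the nose rows of Table 2, or justify it. The length of any look-back for the nose and the merely adjacent regions is for the sponsor to decide.
4. For subjects already enrolled, use the baseline prior-treatment record to flag those with a procedure in a Table 2 region in the previous 12 months, and report the 6-month GAIS with and without them. This needs no new data collection if region and date were captured.

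The cost is a short amendment, a somewhat smaller recruitable pool and one extra table. A blanket 12-month bar on every Table 2 region would cost more recruitment, and the argument above does not require it.

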Chin retrusion: For both men and women, good chin projection and a youthful jawline are considered the standards of beauty and can influence an individual's psychosocial well-being¹⁰. The shape and projection of the chin contribute to a "well-balanced and harmonious" face. Although congenital elements are the predominant factor in chin aesthetics, aging can result in bony resorption and produce sagging as well as laxity and droop in the chin area. In addition, aging can result in bulges and depressions in the pre-jowl sulci.

Temple hollowing: Temple hollowing with associated upper facial thinning is a common feature of the aging face¹¹. Narrowing of the upper facial dimensions is a recognized aesthetic issue in

subjects with human immunodeficiency virus (HIV)-related and antiretroviral therapy-related lipoatrophy. The temple is also a standard site of inclusion during Coleman autolog fat transfer for rejuvenation.

Hyaluronic acids (HAs) have been extensively investigated in the areas to be treated in the present Maili Volume and Maili Extreme study namely midface, temple, chin and jawline. As examples, some of the most recently published studies among the numerous related ones are mentioned hereafter to document the safety/efficacy of HAs in those indications.

Generally, the HAs used in the facial volume deficit conditions (i.e. mid-face volume deficit, jawline ptosis, chin retrusion, and temple hollowing) have particular rheological properties with a high G' value. These HAs are injected at the subdermal or supraperiosteal planes and Global Aesthetic Improvement Scale (GAIS) is one of the main criteria used for evaluation. Moreover, they are long lasting their effects often measured up to 18 months - 2 years.

Two recent VYCROSS HAs can illustrate the targeted effects. In midface deficit the reference is Juvederm Voluma the first HA to obtain an FDA approval in this indication and object of several studies¹²⁻¹³. In addition, this HA was also recently investigated for correction of chin augmentation¹⁴.

For the chin, Juvederm Volux, another recently developed HA, was Food and Drug Administration (FDA) approved in this indication. A recent study evidenced its effect on chin and jaw restoration, which are often tested together¹⁵.

The temples are also an important element of facial rejuvenation and HAs are largely used for volumization of this area. The effect of NASHA HA Restylane, which is another category of HA, has been evaluated ¹⁶.

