- Do not inject subjects having known risk of hypersensitivity to hyaluronic acid or lidocaine or amide local anaesthetics.
- Do not inject subject having history of severe allergy or anaphylactic shock.
- Do not inject subjects suffering from autoimmune disease.
- Do not inject subjects suffering from porphyria.
- Do not inject subjects having cutaneous disorders, inflammation or infection (herpes, acne, etc.) at the treatment site or nearby.
- Do not inject subjects for whom the medical history shows a sensitivity that could lead to a reaction to the treatment.
- Do not use in subjects with bleeding disorders or in subjects who are undergoing treatment with thrombolytics or anticoagulants.
- Do not inject subjects with a tendency to form keloids, hypertrophic scars or any other healing disorders.
- Warn subjects who have a medical history of herpes zoster of the potential risk of reactivation before deciding to participate in the study.
- Do not use during pregnancy or breast-feeding.
- Do not use for children.
- Do not inject into blood vessels (intra-vascular) or directly near blood vessels (for avoiding vessels compression). An unintended intravascular administration can cause high blood concentration and acute central nervous system and cardiovascular toxic symptoms.
- Do not inject in area other than the face (e.g. hands, body).
- Do not inject MaiLi Volume/Extreme in the periorbital area (eyelids, palpebromalar groove, crow's feet) and glabellar region.
- The injection of MaiLi Volume/Extreme into the subcutaneous fat tissue or into the supraperiostic zone is reserved to specialists specifically trained in these injection techniques.
- Do not inject intramuscularly. There is no available clinical data about injection of MaiLi Volume/Extreme into an area which has already been treated with another brand of resorbing product. It is therefore recommended not to inject in areas in which another brand of resorbing
- product is not still fully resorbed.
- Do not inject jointly with another brand of resorbing product in the same area.
- Do not inject jointly with a permanent product.
- Do not mix with other products.
- Do not re-sterilise the product (the syringe and/or the needle).
- Do not inject more than 20 mL per year per subject.
- Do not inject more than 2 mL per treatment area during each session.
- Do not overcorrect.
- Do not use after expiry date or if the packaging is damaged or the syringe opened.

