Blindness. Blindness due to periocular embolism of HA is instant and associated with excruciating ocular pain. The retinal circulation needs to be restored within 60 to 90 minutes if the retina is to survive. Blindness is a medical emergency and the patient should be transferred immediately to the nearest hospital eye department (Refer to the ACE Group guidance on blindness¹⁸). Retrobulbar injection of hyaluronidase (150–200 units in 2–4mL of diluent) into the inferolateral orbit¹⁹ should be considered by practitioners who have appropriate experience and competence while waiting for an ambulance. Treatment of blindness is rarely successful.¹⁹

Tyndall effect. The Tyndall effect refers to the scattering of light that may be seen in some patients after injection of HA resulting in a bluish hue of the skin and most commonly seen in the sub ocular region. The problem can be resolved using hyaluronidase (Refer to ACE Group guidance on the Tyndall effect²⁰).

Unacceptable cosmetic outcome.

Overcorrection or misplacement of HA filler can be successfully treated with hyaluronidase, although this is often caused by poor injection technique or poor choice of product for a particular indication. If HA is present, then hyaluronidase is effective, and HA gel has been successfully removed 63 months post-treatment.²¹

Delayed onset nodules. Lumps or nodules that appear several months after the initial treatment might be amenable with hyaluronidase (Refer

to ACE Group guidance on delayed onset nodules ²²). It is important to remember that hyaluronidase is used to help diffuse fluids intradermally and for hypodermoclysis. To prevent potential dissemination of infection in inflammed nodules, it is important to prescribe antibiotics for one week before administering hyaluronidase.

Allergic or immunogenic reaction to the HA dermal filler. When an allergic, immunogenic, or sensitivity reaction occurs and does not settle on its own within an acceptable amount of time following a short course of antihistamines or systemic corticosteroids, removal of the filler with hyaluronidase is appropriate. If the reaction is considered moderate or severe, oral corticosteroids should be taken before hyaluronidase use to manage or prevent the potential initial worsening of symptoms due to the increase in antigens as the HA is broken down.

STORAGE AND RECONSTITUTION

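### Exclusion 1d applies a 12-month look-back to permanent filler, so a subject with older permanent filler in the region to be treated is eligible

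*Protocol*

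**What the plan says.** Protocol section 4.4 opens exclusion 1 with one stem, "Subjects who, in the twelve months prior to their enrolment assessment had undergone", which governs items a to g. Item d is "augmentation with any permanent or semi-permanent filler (e.g., silicone, PMMA, PLLA) or temporary filler (e.g., Ha, CaHA, PCL". A closing line limits all seven items to the region to be treated. The synopsis carries the same item under the same stem ("augmentation with any permanent or semipermanent filler (e.g., silicone, PMMA, PLLA"). The synopsis also states the eligibility rule: a subject qualifies by meeting every inclusion criterion and no exclusion criterion.

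The contraindications and warnings in section 5 deal with earlier or concurrent fillers separately from eligibility. On permanent products the whole text is "Do not inject jointly with a permanent product". On resorbing products there are two statements. One bars joint injection with another brand in the same area. The other concerns product left over from before: "It is therefore recommended not to inject in areas in which another brand of resorbing" product has not yet fully resorbed.

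Safety is part of the primary objective (section 2.1), through collection of all adverse events. Section 3 names nodules, abscesses and granulomas among the possible effects of the study products.

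**The concern.** A look-back window works as a washout. It makes sense where the earlier product, or its effect, can be expected to fade. For a product described as permanent, passing month 12 changes nothing about what lies in the tissue. Placing permanent filler in the same item and under the same window as temporary filler therefore gives a rule that does not do what it appears to do.

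What is at stake is attribution. Subjects are recruited among people who attend the clinics for aesthetic procedures (section 4.2), so earlier filler is plausible. Follow-up lasts 24 months, and local filler events can come late. Appendix 8, writing about hyaluronic acid filler, says "Lumps or nodules that appear several months after the initial treatment might be amenable with hyaluronidase". If a nodule or granuloma appears in an area that holds both an old permanent filler and the study product, the investigator may be unable to say which one caused it.

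**Working it through.** The documents give no figure to reproduce here, so the check is a reading of the criteria against a test case, followed by a look at which counts could move.

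1. **Does any criterion catch old permanent filler?** Take a subject with permanent filler placed in the chin 13 months before the enrolment assessment.
   - Exclusion 1d: 13 > 12, so it is not met.
   - Exclusion 2 concerns procedures during the study period, so it is not met.
   - Exclusions 3 to 17 do not mention earlier augmentation. Exclusion 14 would catch a region that is inflamed or infected at screening, whatever the cause, but not a quiet filler.
   - The inclusion criteria (section 4.3) ask for a visible deficit, consent and compliance. None asks about earlier filler.
   - Result: eligible.

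   If the same filler had been placed 11 months before, 11 < 12 and the subject is excluded. Both subjects carry a permanent product. Only the elapsed time differs, by 13 − 11 = 2 months.

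2. **Does section 5 close the gap?** Set the warnings side by side:
   - Resorbing product: one rule on joint injection, and a separate recommendation on residual product.
   - Permanent product: the joint-injection rule only.

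   Section 5 thus treats joint use and residual product as two different matters, and for permanent filler it addresses only the first. The natural reading of *jointly* is concurrent use. If it is read more widely, to include filler already in place, then 1d admits subjects whom section 5 says not to inject. Under either reading the criterion needs the same edit.

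3. **Which counts could move?**
   - All-cause adverse events: section 6.1.2 counts an event whether or not it is related to the device. Change from misattribution = 0.
   - Adverse device effects: section 6.1.3 requires a relation to the device, so this count depends on the causality call. Suppose m late local events occur in areas that also hold permanent filler and cannot be separated by cause. The count may then include anywhere from 0 to all m of them.
   - Direction: section 6.2.1 lists an effect of another device among the grounds for calling an event unrelated, which would lower the count. It also sends cases that cannot be assessed to the *possible* category, which would raise it. Both rules are worded for serious events.
   - Size: m depends on how many of the 168 recruited subjects carry older permanent filler in a treated region and on their event rate. The documents give neither, so m cannot be derived.

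**The case against.** The strongest reply is that treatment is already controlled. The investigator takes a medical history before eligibility is settled, prior treatments are recorded at baseline (Table 8), and the section 5 warnings are in front of the same person. The word *jointly* is not defined, and a careful investigator may well decline to inject over old silicone. Section 6.2.1 also tells assessors to weigh confounding factors. Further, no part of the protocol says that injecting hyaluronic acid over long-standing permanent filler is harmful: section 3 describes effects of the study products, and Appendix 8 concerns hyaluronic acid filler. Finally, a post-market study can reasonably want a broad population.

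Much of this stands, and it limits how much weight the point can carry. It does not remove the gap. Leaving the matter to individual judgement at four sites is different from having a criterion, and the criterion as written signals that permanent filler older than 12 months is acceptable.

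A reader might go further and infer that 12 months is also too short for resorbing fillers. The documents do not support that. Section 5 already recommends against injecting where another brand is not fully resorbed, and nothing prevents applying this at screening. The background statement "Moreover, they are long lasting their effects often measured up to 18 months - 2 years" is about effect, not resorption. The Appendix 8 remark that "HA gel has been successfully removed 63 months post-treatment" is a single statement without a frequency. It shows that persistence can happen, not that a 12-month minimum is wrong.

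**Conclusion.** The point holds in a narrow form. Criterion 1d, in section 4.4 and in the synopsis, applies a time limit to a product that the protocol itself calls permanent, and no other criterion reaches such filler once 12 months have passed. It is a cheap improvement to the wording of eligibility, not a flaw that threatens the trial.

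Its size is bounded on one side only: the all-cause adverse event count changes by 0. The effect on the adverse device effect count is unknown in size and direction. The conclusion assumes that permanent means what it says and that the filler has not been removed. It does not depend on which of the listed examples counts as permanent.

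A reader might infer that 1d contradicts section 5, or that the safety results will be biased. Neither follows. The section 5 warning most naturally concerns concurrent use, so the two texts leave a gap between them and do not clash. No bias can be claimed when neither the number of affected subjects nor the direction of attribution is known. No efficacy consequence is claimed either, since the Global Aesthetic Improvement Scale and the photographic scales compare each subject with their own baseline.

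**What to change.** In section 4.4 and in the synopsis, take permanent filler out of the 12-month item and make it a separate exclusion: any history of permanent filler in the region to be treated, with no time limit. State which products count as permanent, since the present list of examples mixes permanent and semi-permanent ones without sorting them. Keep the 12-month window for semi-permanent and temporary fillers, and note that the existing section 5 recommendation on full resorption is to be applied at screening.

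No new procedure is needed, because medical history and prior treatments are already collected at baseline. The cost is a wording change in two places, slightly more screen failures and a slightly narrower post-market population. The number of extra screen failures cannot be estimated from the documents.
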